6.1	Schedule of Evaluations	10
6.2	Description of Evaluations	10
6.2.1	Screening Evaluation	10
6.2.2	Enrollment, Baseline, and/or Randomization	10
6.2.3	Follow-up Visits	10
6.2.4	Completion/Final Evaluation	10
7	SAFETY ASSESSMENTS	11
7.1	Adverse Events and Serious Adverse Events	11
7.1.1	Reporting Procedures	11
7.1.2	Follow-up for Adverse Events	12
7.2	Safety Monitoring	12
8	INTERVENTION DISCONTINUATION	12
9	STATISTICAL CONSIDERATIONS	13
9.1	General Design Issues	13
9.2	Sample Size and Randomization	13
9.2.1	Treatment Assignment Procedures	14
9.3	Interim analyses and Stopping Rules	14
9.4	Outcomes	14
9.4.1	Primary outcome	14
9.4.2	Secondary outcomes	15
9.5	Data Analyses	15
10	DATA COLLECTION AND QUALITY ASSURANCE	15
10.1	Data Collection Forms	15
10.2	Data Management	16
10.3	Quality Assurance	17
10.3.1	Training	17
10.3.2	Monitoring	17
11	PARTICIPANT RIGHTS AND CONFIDENTIALITY	18
11.1	Institutional Review Board (IRB) Review	18
11.2	Informed Consent Forms	18

11.3	Participant Confidentiality	19
11.4	Study Discontinuation.....	20
12	ETHICAL CONSIDERATIONS.....	20
13	COMMITTEES.....	20
14	PUBLICATION OF RESEARCH FINDINGS	21
15	REFERENCES.....	21
16	SUPPLEMENTS/APPENDICES	23

PRÉCIS

Study Title

Effect of an Advance Care Planning Intervention on Documentation of Advance Directive Orders

Objectives

The primary objective of this embedded, pragmatic, cluster-randomized trial (ePCT) is to test the effects of an advance care planning (ACP) intervention on documentation of do-not-resuscitate (DNR) orders in a target cohort of assisted living community (ALC) residents with dementia from 160 ALCs in FL, MN, and WI.

We will also be conducting semi-structured interviews with Bluestone clinicians and staff from 18 ALCs, to describe: (1) the ACP process with ALC patients and their families, and how changes in advance directives are communicated to ALC staff; (2) impressions of the ACP intervention; and (3) challenges to honoring resident advance directives in the ALC setting

Design and Outcomes

ALC residents who are “full code” or do not have a documented code status in their electronic health record (EHR) at baseline will be randomly assigned to Usual care or ACP informational packet and video sent electronically to resident or proxy.

The primary clinical outcome will be the proportion of residents with DNR orders in the EHR at the end of four months followup. Secondary clinical outcomes will be: proportion of residents with do-not-hospitalize (DNH) orders in the EHR at the end of four months followup; proportion of residents with Medicare CPT billing code for ACP during the four months followup; and proportion of enrolled residents with any hospitalizations over four months (outcome available for FL ALCs only). Implementation outcomes include counts of emails sent and video views.

Interventions and Duration

ALCs recruited for the study share a common clinician service group, Bluestone Physician Services (Bluestone). Bluestone delivers 800-900 physician visits per day, including urgent care and COVID-19 testing. Delivery of the intervention leverages a component of Bluestone’s EHR infrastructure, an online portal used to share resident clinical updates with family members, ALC staff, and other members of the resident’s care team (hospice, home health, etc.). This ePCT has two arms: usual care or ACP information .

ACP Information:

Patient centered medical home (PCMH) specialists at Bluestone will determine who is the correct person to receive the informational materials. If the patient is the correct recipient, Bluestone will deliver the informational materials to the resident at the ALC. If

the proxy is the correct recipient, the PCMH specialist will determine whether or not the proxy is using the existing online portal. If the proxy is using the portal, the informational materials will be sent electronically. If the proxy does not access the portal, the informational materials will be sent to their residences.

The informational materials include an email with a link to a video highlighting the goals of care and their relationship to common treatment decisions including resuscitation, hospitalization, antibiotic use, and feeding tubes. For patients and proxies who are not using the online portal, a cover letter and brochure with the same information contained in the video will be mailed. Materials will be available in English and Spanish.

Usual Care: ALC patients and proxies randomized to the usual care arm have ACP discussions with a clinician at admission, annually, and sometimes with a hospitalization or other change in condition. There is no standardized decision- or conversation-support tools used to have these discussions.

Sample Size and Population

Based on baseline Bluestone data, for the 100 already randomized facilities, we expect 54% of residents in the control arm will have a DNR order at the end of 4-months followup. Based on the same data, we estimated an ICC of 0.012. Assuming a conservative ICC of .02, to achieve a power of .80, we need 71 ALCs per arm with 10 PLWD in each to demonstrate an 8-percentage point increase in DNR orders, such that information outreach would result in 62% of these residents having a DNR order at the end of 4-month follow-up.

For the additional 60 facilities, we expect only 26% of the residents in the control arm will have DNR order at the end of 4-months follow-up based on baseline Bluestone data (similar ICC to previously randomized facilities). Assuming a conservative ICC of .02, to achieve a power of .80, we need 79 ALCs per arm with 10 PLWD in each to demonstrate a 7-percentage point increase in DNR orders, such that information outreach would result in 33% of these residents having a DNR order at the end of 4-month follow-up.

We will add 30 ALCs to the existing 50 ALCs per arm, resulting in 80 ALCs per arm. We will be able to detect between a 7- and 8-percentage point change in documentation of DNR orders in the EMR. Our primary approach will be an intention-to-treat (ITT) analysis.

STUDY TEAM ROSTER

Collaboratory Principal Investigator:

[name]., M.P.H.
Professor of Medicine, Harvard Medical School
Senior Scientist, Hebrew Senior Life Institute for Aging Research
[name]
[name]
[contact]
[contact]

Supplement Principal Investigator:

[name]
Assistant Professor
Center for Gerontology and Healthcare Research
Health Services, Policy & Practice
Brown University, School of Public Health
[name]
[name]
[contact]
[contact]

Co-Investigators:

[name]
Associate Professor of Biostatistics
Brown University, School of Public Health
[name]
[name]
[contact]
[contact]
role: co-Investigator, statistical design and analysis lead

[name]
Associate Director, Center for Long-Term Care Quality & Innovation
Associate Professor of Practice, Department of Health Services, Policy & Practice
Center for Gerontology and Health Care Research
Brown University, School of Public Health
[name]
[contact]
[contact]
Role: co-Investigator, process evaluation co-lead

[name]
Assistant Professor

Center for Gerontology and Healthcare Research
Health Services, Policy & Practice

1 STUDY OBJECTIVES

1.1 Primary Objective

The primary objective of this embedded, pragmatic, cluster-randomized trial (ePCT) is to test the effects of an advance care planning (ACP) intervention on documentation of do-not-resuscitate (DNR) orders in a target cohort of assisted living community (ALC) residents with dementia from 160 ALCs in FL, MN, and WI.

1.2 Secondary Objectives

The secondary objective is to use semi-structured interviews with Bluestone clinicians and staff from 18 ALCs to describe: 1) the virtual ACP process with ALC residents and their families, and how changes in advance directives are communicated to ALC staff; (2) impressions of COVID-specific ACP intervention; and (3) challenges to honoring resident advance directives during the coronavirus pandemic.

2 BACKGROUND AND RATIONALE

2.1 Background on Condition, Disease, or Other Primary Study Focus

Assisted living communities (ALCs) serve over 800,000 vulnerable older adults at high risk of developing complications and dying from COVID-19. Most ALC residents are 85 years of age or older and require assistance with bathing and dressing. Over 80% of ALC residents have three or more chronic conditions, and ALC and long-stay nursing (NH) residents have similar rates of diabetes, chronic obstructive pulmonary disease (COPD), and heart failure. Up to 70% of ALC residents have Alzheimer's Disease and Related Dementias (ADR). In normal times, 43% of ALC residents are transferred in the last 30 days of life and 16% die in hospital. However, ALC residents with dementia and other comorbid conditions are especially susceptible to the most serious respiratory complications of COVID-19, and the least likely to benefit from hospital level care.

Unlike nursing homes, ALC residents contract separately for most medical services, which are delivered by external provider groups. Bluestone Physician Services, an existing partner under the National Institute on Aging IMPACT Collaboratory (U54AG063546), provides medical services in approximately 1,000 ALCs across three states (MN, WI, and FL). In the face of the coronavirus pandemic, Bluestone has rapidly transitioned from an on-site population health management model to remote care delivery. Bluestone is delivering 800-900 virtual physician visits per day, including urgent care and COVID-19 testing.

Documenting preferences in the form of an advance directive or medical order, reduces receipt of unwanted care. In the face of the current pandemic, it is critically important to optimize advance care planning (ACP) and documentation of advance directives. ALC residents and their proxies must understand the course of COVID-19, treatment options if complications develop, and potential outcomes of these treatment options to make informed choices about their advance directives, particular as they relate to their preferences for hospital transfer and artificial ventilation.

2.2 Study Rationale

A major long-term care priority in response to COVID-19 is increased use of resident advance directives. Despite an overwhelming patient and caregiver preference for comfort-focused end-of-life care, 43% of ALC residents are transferred in the last 30 days of life and 16% die in hospital. In the face of COVID-19, Bluestone understands the urgent need to increase advance directive ascertainment and documentation in their ALCs, particularly for their most vulnerable residents, such as the 69% of their residents with dementia. Bluestone is unique among ALF providers in that it has an integrated electronic health record (EHR) with a HIPAA-compliant feature that allows its physicians to communicate information about residents to family members, ALC staff, and other members of the resident's care team. Bluestone's EHR data contain detailed information on resident physical and cognitive function, chronic conditions (including dementia diagnoses), and documentation of advance directives. We will leverage this infrastructure to conduct a 1-year trial of an ACP intervention directed toward residents and families of ALC residents with dementia.

3 STUDY DESIGN

This is a one year, embedded, pragmatic cluster-randomized trial (ePCT). ALCs will be randomly assigned to Usual care or ACP informational website and video sent electronically to family members. Stratifying by state and balancing on baseline use of DNR orders, number of Bluestone residents in the ALC, and resident clinical characteristics, a Brown statistician will randomize 160 ALCs to the intervention or control study arms (80 ALCs per arm).

Information materials include an email (Appendix A) with a link to a video describing resident goals of care and instructions for documenting treatment preferences in the form of advance directives or medical orders (Appendix B). When patients or proxies are not using the online portal, a letter and brochure reflecting the same content as the video will be sent to their residences. The materials were developed by [name], [name] and colleagues at Indiana University. [name] has agreed to modify their materials for the purposes of the study. In addition, all Bluestone clinicians will receive training (Appendix C) and a tailored conversation guide to help structure conversations with patients or proxies, when appropriate (Appendix D).

Residents and family members of eligible residents in ALCs randomized to the usual care arm have ACP discussions with a clinician at admission, annually, and sometimes with a hospitalization or other change in condition. There is no standardized decision- or conversation-support tools used to have these discussions. Clinicians will engage PLWD in advance care planning discussions as they would in usual care.

The primary clinical outcome will be the proportion of residents with DNR orders in the EHR at the end of four months followup. Secondary clinical outcomes will be: proportion of residents with do-not-hospitalize (DNH) orders in the EHR at the end of four months followup; proportion of residents with Medicare CPT billing code for ACP during the four months followup; and proportion of enrolled residents with any hospitalizations over

four months (outcome available for FL ALCs only). Implementation outcomes include counts of physician calls with family members and counts of website and video views. We plan to enroll approximately 3,000 patients and/or their proxies.

Our partner health care systems will know which ALCs are randomized to each arm. Brown University statistician and data management staff will present aggregated post-random assignment comparisons of intervention and control facilities' baseline characteristics, but these preliminary analyses will be not generated at the individual facility level. Drs. [name] and [name] will be blinded. ALC assignment will be unblinded to the DSMB members at their request.

We will also be conducting semi-structured interviews with Bluestone clinicians and staff from 16 ALCs, to describe: 1) the ACP process with ALC patients and their families, and how changes in advance directives are communicated to ALC staff; (2) impressions of the ACP intervention; and (3) challenges to honoring resident advance directives in the ALC setting

4 SELECTION AND ENROLLMENT OF PARTICIPANTS

4.1 Inclusion Criteria

The unit of random assignment will be the ALC and the unit of analysis the resident, clustered within the ALC. We will use Bluestone's EHR data to identify eligible ALCs. Eligible ALCs will have at least 10 patients with a dementia diagnosis (ICD-10) who are not on hospice and do not have orders for comfort care or DNH at baseline.

4.2 Exclusion Criteria

ALCs with less than 10 patients with a dementia diagnosis (ICD-10) who are not on hospice and do not have orders for comfort care only or DNH baseline will be excluded from the study. Further, Bluestone may exclude ALCs prior to randomization based on knowledge of competing ACP initiatives or any other concerns about their relationship with the ALC.

4.3 Study Enrollment Procedures

This is an ePCT in which Bluestone will be responsible for enrolling participants. We are asking for a waiver of informed consent on Bluestone's behalf. Per 45 CFR §46.116 f 3 (i-v), we believe that:

(i) The research involves no more than minimal risk to the subjects; The only risk to the broad group of individuals for whom we are requesting the EHR data is the risk of breach of confidentiality and we have described our security procedures for minimizing this risk. We also believe there is minimal risk to the subset of individuals who will be subjected to the intervention itself. The intervention will consist of three arms - a control arm (usual care); treatment arm 1 where eligible residents in ALCs randomized to the information arm will receive a letter from their Bluestone physician with links to an informational website and advanced care planning (ACP) video sent through the online portal; and treatment arm 2 where eligible residents will receive the same outreach letter from their Bluestone physician with links to the informational website and video in addition to a follow-up phone call by their Bluestone physician to have a structured conversation about

ACP with families. ACP is something that is routinely discussed between physicians and patients and their caregivers. This intervention, which examines the effectiveness of two modes of delivery for the discussion compared to usual care, does not increase the level of risk beyond what an individual would encounter in usual care.

(ii) The research could not practicably be carried out without the requested waiver or alteration; There is no need for the research team to have contact with study subjects for this study. Recruitment and selection can be done passively through the use of EHR and the physician offices will be sending the letters and making the clinical phone calls in the two treatment arms directly. It would not be practicable to contact individuals for informed consent.

(iii) If the research involves using identifiable private information or identifiable biospecimens, the research could not practicably be carried out without using such information or biospecimens in an identifiable format; The data could not practicably be sent to the research team without identifiers because we will be following individuals over time and must be able to link their information longitudinally. In addition, we must be able to identify EHR records within specific locations in order to recruit facilities as well as tell physicians which patients to include in the intervention.

(iv) The waiver or alteration will not adversely affect the rights and welfare of the subjects; and We do not believe the waiver or alteration will adversely affect the rights and welfare of the subjects. The physicians who will be involved in the intervention already have access to the patients' EHR for routine clinical care purposes and will be reaching out to them as they would in regular practice. Patients are free to ignore the informational letter and not engage with the physician in an ACP discussion. The EHR data used will be securely stored and kept confidential. Direct identifiers will be removed by Brown Center for Gerontology and Health Care Research IT Director and replaced with study IDs prior to release to the study team for analysis. All results will be presented in aggregate. No individual information will be released.

(v) Whenever appropriate, the subjects or legally authorized representatives will be provided with additional pertinent information after participation. We will provide Bluestone with copies of reports and manuscripts that result from this project. They are free to share information with their clinicians and facilities. The clinicians and facilities are free to share the information with interested families and patients.

For the process evaluation, will ask Bluestone leadership to nominate eight physicians to participate in semi-structured interviews. The research assistant will contact the physicians recommended by corporate leadership, explain the study, and provide an opt-out for participation. We will use the baseline EHR data to identify eight ACLs (one for each physician interviewed) with varying baseline AD use. Bluestone leadership and/or the physician working in the ALC will approach the director to ask if s/he would participate in an interview. The director will nominate a member of the direct care staff for interview.

5 STUDY INTERVENTIONS

5.1 Interventions, Administration, and Duration

Delivery of the intervention leverages a component of Bluestone's EHR infrastructure, an online portal used to share resident clinical updates with family members, ALC staff, and other members of the resident's care team (hospice, home health, etc.). This ePCT has two arms: usual care and ACP information.

Information Only:

Patient centered medical home specialists at Bluestone will determine who is the correct person to receive the informational materials. If the patient is the correct recipient, Bluestone will send the informational materials to the resident at the ALC. If the proxy is the correct recipient, the clinical assistant will determine whether or not the proxy is using the existing online portal. If the proxy is using the portal, the informational materials will be sent electronically. If the proxy does not access the portal, the informational materials will be sent to their residences.

The informational materials include an email with a link to a video highlighting the goals of care and their relationship to common treatment decisions including resuscitation, hospitalization, antibiotic use, and feeding tubes. For patients and proxies who are not using the online portal, a cover letter and brochure with the same information contained in the video will be mailed. Materials will be available in English and Spanish.

Usual Care: ALC patients and proxies randomized to the usual care arm have ACP discussions with a clinician at admission, annually, and sometimes with a hospitalization or other change in condition. There is no standardized decision- or conversation-support tools used to have these discussions.

5.2 Handling of Study Interventions

Our partner, Bluestone, will know which ALCs are randomized to each arm. Brown University statistician and data management staff will present aggregated post-random assignment comparisons of intervention and control facilities' baseline characteristics, but these preliminary analyses will be not generated at the individual facility level. Drs. [name] and [name] will be blinded. ALC assignment will be unblinded to the DSMB members at their request.

5.3 Concomitant Interventions

This is a pragmatic study. It is possible that ALCs enrolled in this study may be participating in other ACP interventions. We do not expect participation in competing interventions will differ between treatments and control arms. When Bluestone is aware of such interventions, they may choose to exclude ALCs prior to randomization. It is also possible that Bluestone physicians may work in ALFs randomized to different study arms. We will work to limit this contamination through the randomization process. We expect the effect of this potential contamination to be limited as clinical assistants will

only send informational materials to patients randomized to the information only arm and physicians will only call patients / proxies whom they are instructed to call.

5.4 Adherence Assessment

Adherence outcomes include number of emails sent to patients / proxies and the number of clicks to follow links for informational website or video, and number of patients / proxies.

6 STUDY PROCEDURES

There will be 80 ALCs in each study arm. The outcome follow-up time for this intervention is four months. If the outreach intervention works, we expect orders to change shortly after the physician and patients or proxies have a discussion.

6.1 Schedule of Evaluations

Table 1. Project Timeline

Workgroup	Task	2021												2022		
		Jan	Feb	Mar	Apr	May	Jun	Jul	Aug	Sep	Oct	Nov	Dec	Jan	Feb	Mar
Data	Ongoing transfers of EHR data to Brown	X	X	X	X	X	X	X	X	X	X	X	X	X	X	X
Data	ALC eligibility and randomization	X	X	X								X				
Data	Ongoing eligibility list transfer from Brown to Bluestone	X	X	X	X	X	X	X	X	X	X					
Aim 1	Finalize intervention materials	X	X	X												
Aim 2	Finalize interview guides				X	X										
Aim 2	Identification of providers and AL staff for interviews					X	X									
Aim 1	Intervention roll-out: rolling study enrollment, 4-month follow-up			X	X	X	X	X	X	X	X	*	*			
Aim 1	Intervention roll-out to newly added facilities, 4-month follow-up										X	*	*	*	*	
Aim 2	Process evaluation interviews							X	X	X						
Aim 2	Transcribe interviews									X	X	X				
Aim 2	Analyze interviews											X	X			
Aim 1	Unblinding and evaluation of study primary & secondary outcomes											X	X	X	X	
Aim 1 & 2	Dissemination of results													X	X	

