9.4 Outcomes

9.4.1 Primary outcome

The primary clinical outcome will be the proportion of residents with DNR orders in the EHR at the end of four months followup.

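### The timeline marks unblinding and outcome evaluation while the 60 added ALCs are still in four-month follow-up, and no text makes unblinding wait for completion

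*Combined protocol and SAP*

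**What the plan says.** Table 1 (Project Timeline) in Section 6.1 has a row beginning "Unblinding and evaluation of study primary", which continues to the secondary outcomes. It is marked in November and December 2021 and January and February 2022.

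The row for the added ALCs, "Intervention roll-out to newly added facilities, 4-month follow-up", has an X in October 2021 and an asterisk in each of the next four months, November 2021 to February 2022.

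Section 6 states: "The outcome follow-up time for this intervention is four months". Section 9.4.1 defines the endpoint accordingly: "The primary clinical outcome will be the proportion of residents with DNR orders in the EHR at the end of four months followup". Section 9.2 adds 30 ALCs per arm to the existing 50 and sizes the trial as one comparison of 80 per arm. Section 9.3 says there will be no interim analysis.

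On the timing of analysis, Section 10.3.2 says only that the analyst runs the outcome analyses, under a pre-specified plan, once the data files are ready. The study PI and the Collaboratory's principal investigators stay blind during that work. Sections 3 and 5.2 add that certain investigators are blinded and that the DSMB may see assignments on request.

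**The concern.** Every month set aside for opening and evaluating the outcomes is also a month in which the added ALCs are marked as being followed. For most of that window their primary outcome cannot yet exist. A team working to the schedule could compare the arms while more than a third of the clusters are incomplete. That would be an early look which Section 9.3 says will not happen, and the plan has no rule relating it to the final 160-ALC result. The schedule is the only place where the documents date unblinding, so the rest of the text does not correct it.

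**Working it through.** **Inputs.** The marks come from Table 1 in Section 6.1, read by column position over its 15 months (January 2021 to March 2022). The follow-up length comes from Sections 6 and 9.4.1, and the cluster counts from Section 9.2. The asterisk has no legend in the available text. It is read as follow-up because the row label names follow-up and exactly four asterisks come after the October X, matching the four-month period.

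| Row of the timeline | Marks |
|---|---|
| Eligibility and randomisation of ALCs | X Jan–Mar 2021 and Nov 2021 |
| Eligibility-list transfer | X Jan–Oct 2021 |
| First-wave roll-out and follow-up | X Mar–Oct 2021, * Nov–Dec 2021 |
| Added ALCs, roll-out and follow-up | X Oct 2021, * Nov 2021–Feb 2022 |
| Unblinding and outcome evaluation | X Nov 2021–Feb 2022 |
| Dissemination, Aims 1 and 2 together | X Jan–Feb 2022 |
| EHR transfers | X Jan 2021–Mar 2022 |

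**Share of the trial affected.** 2 × 30 = 60 added ALCs and 2 × 80 = 160 in total, so 60/160 = 37.5%.

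**Overlap.** All 4 evaluation months carry an asterisk for the added ALCs. None falls after their last asterisk.

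**When the added ALCs reach the endpoint.** Date reached = roll-out date + 4 months.
- 1 October 2021 + 4 months = 1 February 2022.
- 31 October 2021 + 4 months = 28 February 2022 (month end).
- If October itself is month 1, the four months are October to January, and completion is about 31 January 2022.

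By calendar date, no added-ALC resident can have a four-month status in November, December or January. With October as month 1, this covers November, December and nearly all of January. The exception is the Section 9.5 rule, which carries forward the last observed status after death or discharge beyond two months. By calendar date that cannot apply to an added-ALC resident before 1 October + 2 months = 1 December 2021.

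**Other marks that do not fit together.**
- The second mark for "ALC eligibility and randomization" is in November 2021. That is one month after the added ALCs' roll-out and after the last mark for "Ongoing eligibility list transfer from Brown to Bluestone", both in October. If the November mark is right and roll-out followed it, the endpoint dates become 1 to 30 March 2022.
- The first-wave row, "Intervention roll-out: rolling study enrollment, 4-month follow-up", has X marks to October and asterisks only in November and December. If enrolment ran to 31 October, four months ends on 28 February 2022. If enrolment ended on 31 August, it ends on 31 December 2021, which matches the last asterisk. The label joins enrolment and follow-up, so the table does not settle which was meant.

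**The case against.** The best case against the point is that a bar in a project timeline is not an analysis specification. The row joins unblinding with evaluation, so its first month need not be the month of unblinding. It could be blinded data preparation, or work on the first 100 ALCs. Sections 9.3, 9.4.1 and 10.3.2 together point to a single final analysis, with senior investigators blind until it is done. No stopping rule or adaptation depends on an early result.

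Much of this stands, and it lowers the risk. It does not remove the inconsistency. No section limits the early months to preparation or to the first wave. Readiness of the data files is not the same as completed follow-up. The blinding in Section 10.3.2 does not say when the outcome analysis may begin.

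A reader might go further and infer that Aim 1 results would be published during follow-up, because "Dissemination of results" is marked in January and February 2022. The documents do not support that. The row covers both aims, and the Aim 2 interviews are analysed in November and December 2021, so the marks may reflect Aim 2 alone.

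A reader might also infer that early results would reach Bluestone's clinicians and alter the documentation that forms the endpoint. Section 4.3 does let Bluestone receive and share reports, but under the waiver item about information given after participation. Section 14 also requires review by the sponsor and the NIA before anything is submitted. No feedback during follow-up is described.

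**Conclusion.** The point holds as an inconsistency in the operative schedule, and it should be fixed. For 60 of 160 ALCs (37.5%), the primary outcome does not exist in November, December and most or all of January, three of the four months marked for unblinding and evaluation, apart from residents censored under Section 9.5. No section makes unblinding wait for them.

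This rests on the month placement in the extracted table, on reading the asterisk as follow-up, and on October 2021 as the roll-out month. It uses no assumption about enrolment rate, cluster size or power.

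It does not show that an interim analysis is planned or that unblinding is set for November. The later completion dates in March 2022 depend on the November randomisation mark, which may simply be one misplaced mark. The first-wave shortfall depends on enrolment having continued to October. Both are items to check and do not add to the size of the main point.

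**What to change.** State in Section 9.3 that unblinding, any outcome comparison by arm and release of Aim 1 results begin only when two conditions are met. Every enrolled resident in all 160 ALCs must have completed four months or been censored under Section 9.5, and the final EHR transfer must have been received. Move the evaluation marks, and the Aim 1 part of the dissemination marks, in the timeline to match. Blinded data preparation and Aim 2 release can go earlier. If a separate earlier evaluation of the first 100 ALCs is intended, Section 9.3 must name and specify it.

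In the same edit, reconcile the November 2021 randomisation mark with the October roll-out and list-transfer marks. Check that the first-wave asterisks cover four months after the last enrolment, and give the asterisk a legend if the source table has none.

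The drafting is small: one statement in Section 9.3 and corrected marks. The real cost is time. With completion at the end of January, unblinding starts in February 2022, 3 months after the November mark. With completion at the end of February, it starts in March 2022, 4 months after. Evaluation and Aim 1 dissemination may then run to or past March 2022, the last month of the timeline. If the November randomisation mark proves correct, follow-up runs into March and an EHR transfer after that month may be needed. Aim 2 is unaffected.
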